Following the identification of the strongest drug class in chronic PN pain medication at each cycle, the change in score at each cycle compared to baseline will be programmatically identified following the algorithm outlined in Figure 3. If changes in the strongest drug class from baseline do not follow under the categories of Figure 3. of “Increased” or “Decreased,” the category “No Change” will be assigned. For the cycles where no PN chronic medication has been recorded in the eDiary, the change will be set to “Missing”.

A secondary definition for change from baseline in PN pain medication (Increased/Decreased/No Change) is derived using the investigator analgesic requirement assessment recorded on the e-CRF, indicating whether the reason is PN pain or other pain.

Figure 3: PN Pain Medication Score Changes Algorithm

PN, plexiform neurofibroma; WHO, World Health Organisation.

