Distribution of the eDiary entries will be presented for the FAS and the Pain FAS. For the PAINS-pNF (chronic target PN pain and spike PN pain) and the PN pain medication eDiaries, summary tables of eDiary completion rates per cycle (including baseline) and study intervention group will be presented at each cycle (including baseline). The number and percentage (ie, eDiary compliance) of expected daily diary entries is defined as the sum of the number of daily entries expected prior to study treatment discontinuation for all patients on treatment. A daily entry will be considered as completed for PAINS-pNF if a daily PN pain score is recorded. A diary entry will be considered as completed for PN pain medication if the question “Did you take any medication for your tumour pain from the time you went to bed last night until now (including overnight)?” was answered and if the items after it are answered. Additionally, for PAINS-pNF chronic target PN pain, the number of expected daily diary entries and eDiary compliance will be presented by 0, 1, 2, 3, or 4 non-overlapping 7-day periods with at least 4 daily pain scores at baseline and during each 28-day cycle, which is the minimum compliance requirement to calculate a cycle average chronic PN pain intensity score.

For the rest of the PRO instruments, the number of expected forms and the following instrument completion rates at each cycle will be reported by treatment group:

- The number and percentage of patients with all questions completed.
- The number and percentage of patients meeting at least the minimum requirements for scoring of the instrument.
- The number and percentage of patients with at least 1 question completed.

All completion rates will be presented for the FAS, and the denominator will be the number of patients who are expected to have PRO assessments.

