4.2.9 Chronic Target PN Pain Palliation During the Randomised Period

4.2.9.1 Definition

Chronic target PN pain palliation at a cycle is defined as the occurrence of both of the following events:

- 1) Improvement of ≥ 2 in average PAINS-pNF chronic target PN pain intensity score
- 2) No increase in chronic PN pain medication compared to baseline for that cycle
 - i. Assuming that the patient had non-missing chronic PN pain medication data (see Section 4.2.9.4 for definition of “missing”) and did not meet the criteria of eDiary chronic PN pain medication score increase of ≥ 1 compared to baseline (primary definition; see Section 4.2.9.2).
 - ii. Assuming that the patient had non-missing chronic PN pain medication data (see Section 4.2.9.4 for definition of “missing”) and did not meet the criteria of eDiary chronic PN pain medication score increase of ≥ 0.5 compared to baseline (first sensitivity definition; see Section 4.2.9.2).
 - iii. Assuming that the patient had a non-missing investigator electronic case report form (eCRF) assessment (see Section 4.2.9.4 for definition of “missing”) and did not meet the criteria of “increased” due to “PN pain” compared to baseline (second sensitivity definition; see Section 4.2.9.2).

Table 14 summarises the chronic target PN pain definitions that will be examined.

Table 14: Definitions of Chronic Target PN Pain Palliation

Definition	Chronic target PN pain intensity threshold for palliation	Non-missing pain medication data and pain medication increase based on
Primary	2	eDiary chronic PN pain medication score increase of ≥ 1
Sensitivity 1	2	eDiary chronic PN pain medication score increase of ≥ 0.5
Sensitivity 2	2	Investigator’s assessment of “increased” “due to increased PN pain”
Sensitivity 3	From psychometric work*, if different than 2	eDiary chronic PN pain medication increase of ≥ 1
Sensitivity 4	From psychometric work*, if different than 2	eDiary on chronic PN pain medication score of ≥ 0.5
Sensitivity 5	From psychometric work*, if different than 2	Investigator’s assessment of “increased” “due to increased PN pain”

PN, plexiform neurofibroma.

*Psychometric validation of the PAINS-pNF instrument in this study will be performed based on blinded data before DCO1, and a clinically meaningful within-patient change will

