4.2.9.4 Handling of Dropouts and Missing Data

Missing components required for the determination of chronic target PN pain palliation may result if there is:

- Missing average cycle chronic PN pain intensity score for a specific cycle, that is, patients does not have at least 4 out of 7 PAINS-pNF chronic target PN pain intensity scores in at least 3 non-overlapping 7-day periods (same definition as for 1st key secondary endpoint; see Section 4.2.2.1.2);

and/or

- Missing pain medication:
 - 1) For eDiary, missing chronic PN pain medication for all days* (i.e., 28-day cycle) in that specific cycle.
 - 2) For investigator assessment, missing eCRF investigator assessment of analgesic use at that specific cycle.

*For the purposes of this analysis, pain medication data are considered missing *for a day* if the gatekeeper item “Did you take any medication for your usual (chronic) tumour pain from the time you went to bed last night until now (including overnight)?” is “yes” but no pain medications have been entered or the gatekeeper item is missing.

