4.2.11.2 Derivations

For both spike and chronic PN pain medication, the analgesic ladder class and the strongest analgesic ladder score for each cycle will be derived following the scoring algorithm presented in Section 3.3.8. For chronic PN pain, changes from baseline (Increased/Decreased/No Change) will also be derived as outlined in Section 3.3.8.

At each cycle, a binary variable will be derived, set to 1 if a decrease in chronic PN pain medication is observed as per definition in Section 3.3.8 and 0 otherwise. A sensitivity definition of this binary endpoint is derived using the secondary definition of decrease from baseline as assessed by the investigator when the reason for the decrease in analgesic requirement is PN pain.

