4.2.11.4 Handling of Dropouts and Missing Data

For the chronic PN pain medication based on the eDiary, the strongest class of pain medications reported over the 28 days of each cycle will be based on observed scores, that is, days with missing information will be ignored in the derivation.

For purposes of the analysis of decrease in pain medication, 1) if the pain medication data provide sufficient evidence to rule out a decrease for a cycle (see Section 4.2.9.2), that cycle is considered not to have missing pain medication data; 2) if, due to missing *daily*

pain medication data as defined in Section 4.2.9.4, the cycle does not provide sufficient evidence to rule out either an increase or a decrease in pain medication for a cycle, that cycle will be considered to have missing pain medication data.

For the investigator's assessment of change in pain medication, analyses will be based on observed data.

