4.2.11.5 Primary Analysis of Pain Medication

The pain medication decrease during the randomised period will be analysed using a random-effect logistic regression model including treatment, geographical region, and cycle number as fixed effects; baseline chronic PN pain medication score as covariates; and the following interaction terms: treatment-by-cycle number and baseline chronic PN pain medication score-by-cycle number.

A random intercept will also be included to account for variability between patients. An unstructured covariance matrix will be used to allow for unequal treatment variance and to model the correlation between different treatment measurements within the same subject. If the fit of the unstructured covariance structure fails to converge, the following covariance structures will be used in order until convergence is reached: toeplitz with heterogeneity, autoregressive with heterogeneity, toeplitz, autoregressive, and compound symmetry. All main effects and the interaction terms will remain in the model regardless of significance.

The results of the analysis are presented in terms of an odds ratio (selumetinib versus placebo) together with its 95% CI and p-value at each cycle (estimated using the treatment-by-cycle interaction coefficient) and overall, over the randomised period (based on the treatment coefficient). For each treatment arm, the odds will be presented along with the number of non-missing observations used in the estimation (n), the observed number and percentage of responders, and the corresponding 95% CIs. The analysis will be performed on a subset of the FAS population with an evaluable baseline and at least one post-baseline chronic PN pain medication score available. Data collected during the randomised period (see Section 3.3.2.2) adhering to the intercurrent event strategy (refer to Section 4.2.11.3) are included.

This analysis will be repeated using the sensitivity definition outlined in Section 4.2.11.2. For the sensitivity using investigator assessment of analgesic use, the random-effect logistic regression model will include treatment, geographical region, and cycle number as fixed effects; baseline chronic PN pain medication score as covariate; and the following interaction terms: treatment-by-cycle number and baseline chronic target PN pain medication score-by-cycle number.

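### Read literally, the SAP counts complete cessation of chronic analgesics as no decrease in the eDiary medication analysis, because 3.3.8 labels cycles with no recorded medication Missing

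*SAP*

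**What the plan says.** SAP 3.3.8 derives, for each 28-day cycle, the strongest class of chronic PN pain medication in the eDiary and its change from baseline: *Increased*, *Decreased* or *No Change*. It then adds: "For the cycles where no PN chronic medication has been recorded in the eDiary, the change will be set to" *Missing*. Table 2 in the same section runs from 0 to 4, and score 0 is no analgesia.

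Other sections define missing medication data by whether the diary was answered:

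- **SAP 4.2.9.4, day level.** A day is missing if the gatekeeper question is answered *yes* "but no pain medications have been entered or the gatekeeper item is missing". A day answered *no* is therefore not missing.
- **SAP 4.2.9.4, cycle level (palliation).** The eDiary condition is "missing chronic PN pain medication for all days" of the cycle.
- **SAP 4.2.11.4 (decrease analysis).** A cycle is missing when, because of daily gaps in the "pain medication data as defined in Section 4.2.9.4, the cycle does not provide sufficient evidence to rule out either an increase or a decrease".

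The decrease endpoint in SAP 4.2.11.2 is "set to 1 if a decrease in chronic PN pain medication is observed as per definition in Section 3.3.8 and 0 otherwise". It gives no code for a cycle whose change is *Missing*. SAP 4.2.11.5 models this variable in the FAS subset "with an evaluable baseline and at least one post-baseline chronic PN pain medication score available".

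**The concern.** Stopping every chronic analgesic is the largest decrease the ladder can show. A cycle with 28 *no* answers is complete information under 4.2.9.4 and 4.2.11.4, and Table 2 has a score for it. Yet 3.3.8 keys on whether a medication was recorded, not on whether the diary was answered, and so labels that cycle *Missing*. The decrease endpoint then looks to 3.3.8, finds no *Decreased*, and falls to 0.

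At stake is a listed secondary endpoint for which the SAP plans a modelled odds ratio, 95% CI and p-value. The Pain FAS repeat (4.2.11.6), the regional repeats (4.2.11.7) and the China tables (8.5) inherit the same derivation. In the change table, never-users would also appear as *Missing* when their true category is *No Change*.

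**Working it through.** **1. One cycle traced through the rules.** Take a participant with a baseline score above 0 who answers *no* to the gatekeeper question on all 28 days.

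- Table 2: score 0.
- 4.2.9.4: no day is missing, so the cycle is not missing.
- 4.2.11.4: no daily data are missing, so its missing-cycle condition is not met and the cycle stays in the analysis.
- 3.3.8: no chronic medication was recorded, so the change is *Missing*.
- 4.2.11.2: the change is not *Decreased* under 3.3.8, so the endpoint is 0.

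The cycle is thus kept in the model as a non-event, and shown as *Missing* in the change table.

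For a participant at score 0 throughout, the binary code of 0 is correct. Only the change table is wrong.

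**2. How much of the ladder is affected.** From baseline score b there are b lower scores. Downward moves: 1 + 2 + 3 + 4 = 10. One move from each of scores 1, 2, 3 and 4 ends at 0, which makes 4. So 10 − 4 = 6 class-level moves can still be *Decreased* under the literal rule. A participant at baseline score 1 has a single downward move, to 0, and so has no class-level route to a decrease.

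**3. Illustration of the coded-0 result.** The plan states no figure to reproduce, and every input here is assumed: true per-cycle decrease p of 30% on selumetinib and 15% on placebo, and s, the share of decreases that are complete stops. The figures are crude and single-cycle, not the random-effect model of 4.2.11.5.

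- True odds ratio: (0.30/0.70)/(0.15/0.85) = 2.43.
- Stops coded 0: the observed rate in each arm is p(1 − s).
- s = 25% in both arms: (0.225/0.775)/(0.1125/0.8875) = 2.29.
- s = 50% in both arms: (0.15/0.85)/(0.075/0.925) = 2.18.
- s = 75% in both arms: (0.075/0.925)/(0.0375/0.9625) = 2.08.
- s = 50% on selumetinib, 25% on placebo: (0.15/0.85)/(0.1125/0.8875) = 1.39.
- s = 25% on selumetinib, 50% on placebo: (0.225/0.775)/(0.075/0.925) = 3.58.

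Coding stops as 0 lowers the observed decrease rate in any arm where stops occur. The odds ratio can move either way, depending on how stops divide between the arms.

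**The case against.** The best defence is that the 3.3.8 sentence was meant for cycles with no diary data at all. That reading fits Table 2, 4.2.9.4 and 4.2.11.4, and a careful programmer might adopt it. It stands as a plausible intention, but the sentence speaks of medication recorded, not of entries made.

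A second defence is that 4.2.11.4 is written specifically for the decrease analysis and would normally prevail over a general section. A reader might infer that the SAP gives no guidance on precedence; that goes too far, because 4.2.11.4 does say which cycles are missing for this endpoint. But it settles only whether a cycle is missing. The classification as a decrease still comes from 3.3.8 through 4.2.11.2.

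Third, Figure 3, which holds the *Increased*/*Decreased* algorithm, was not visible in the text reviewed. It may class a move to score 0 as *Decreased*. Text and figure would then disagree, and the sentence would still need correcting.

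Fourth, the impact is bounded. The endpoint lies outside the multiple testing procedure. Ladder category and score by cycle are tabulated in 4.2.11.6. The investigator-assessed version does not use the eDiary rule and can record cessation as a decrease. All of this stands.

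One possible support is not relied on. SAP 4.1.1.2 says "A diary entry will be considered as completed for PN pain medication if the question" is answered, but it also requires the items after it to be answered, and does not say how a *no* with no follow-up items counts. It also governs completion tables, not endpoint derivation.

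**Conclusion.** The rules as written give a wrong result: complete cessation is coded as no decrease in the eDiary analysis of 4.2.11.5, and both cessation and never-use appear as *Missing* in the change table of 4.2.11.6. This should be corrected. Confidence is medium because of the benign reading and the unseen Figure 3.

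Three stronger inferences are not supported:

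- **That the estimated effect is biased by a known amount or in a known direction.** The documents give no decrease rate, stop share or never-user share. The odds ratios above show only that the result depends on those unknowns.
- **That these cycles drop out of the model.** That would set aside the residual code of 0 in 4.2.11.2, and 4.2.11.4 does not call a fully answered cycle missing.
- **That the damage reaches the main efficacy claims.** The primary endpoint and the main analyses of the key secondary endpoints do not use this derivation. Although 3.3.8 says its change definition also feeds palliation, 4.2.9.1 sends missingness elsewhere: "Assuming that the patient had non-missing chronic PN pain medication data (see Section 4.2.9.4 for definition of" missing. If 4.2.9.4 governs, as that indicates, palliation is unaffected.

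**What to change.** 1. **SAP 3.3.8.** Replace the sentence with: *A cycle with observed* no *answers to the gatekeeper question and no chronic PN medication taken is scored 0, and its change from baseline is derived. Change is Missing only when daily diary data are missing under Section 4.2.9.4 or, for the decrease analysis, when the cycle is missing under Section 4.2.11.4.* Under this wording, a cycle with a few *no* days among blanks does not count as a decrease where 4.2.11.4 calls it missing.
2. **SAP 4.2.11.2.** Code 1 for decreased, 0 for no change or increased, and missing for a cycle missing under 4.2.11.4.
3. **SAP 4.2.11.6.** State which missing-cycle rule the change table uses. The 4.2.11.4 rule is worded for the decrease analysis only, so this is a choice to be made.
4. **Figure 3.** Confirm that a move from any higher score to 0 is classed *Decreased*.

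The cost is a few sentences in the SAP, one check of a figure and a small programming change. The gatekeeper item is already collected, so no new data are needed.

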3.3.9 Derivation of the Attributability of Reason for Discontinued Randomised Study Intervention

In order to explore the robustness of the inference of the Mixed Model Repeated Measures (MMRM) models of the key secondary endpoints to deviate from the missing at random (MAR) assumption, the number and the reasons for early treatment discontinuations prior to Cycle 12 will be assessed.

Reasons for discontinuation of the randomised study intervention prior to Cycle 12 will be classified as attributable or non-attributable, depending on the potential relationship with study treatment (ie, lack of efficacy or tolerability issues), as per [Table 3](#).

Table 3: Attributable Assessment for Reason of Study Intervention Discontinuation

Non-attributable	Evaluated on case-by-case	Attributable
Technical problems	Non-treatment related adverse event	Treatment -related adverse event
Lost to follow-up	Withdrawal by subject	Progressive disease

Pregnancy	Development of withdrawal criteria	Death
	Important protocol deviation	
	Physician decision	
	Study terminated by sponsor	
	Other	

A complete review of the individual reasons for discontinuation prior to Cycle 12 will be undertaken during a data review meeting of the clinical study team prior to study unblinding to determine the final categorisation.

3.4 Sample Size Determination

Approximately 212 patients will be enrolled to achieve approximately 146 patients randomly assigned to study intervention (either selumetinib or placebo) with a 1:1 ratio (73 patients in each arm).

Randomisation will be stratified by average baseline PAINS-pNF chronic target PN pain score (< 3 and \geq 3) and geographical region (Europe, China, Japan, and Rest of World). The number of patients randomised will be capped at approximately 106 patients with an average baseline PAINS-pNF chronic target PN pain score \geq 3 and approximately 40 patients with an average baseline PAINS-pNF chronic target PN pain score < 3.

Note: “Enrolled” means a patient’s agreement to participate in a clinical study following completion of the informed consent process. Potential patients who are screened for the purpose of determining eligibility for the study but are not randomly assigned/assigned in the study are considered “screen failures,” unless otherwise specified by the protocol.

With a sample size of 73 patients per arm, a Fisher’s exact test with a two-sided alpha of 5% will have >99% power to detect the difference between the selumetinib ORR of 20% and the placebo ORR of 0%. The ORR of 20% in the selumetinib arm by the end of Cycle 16 is assumed from ad hoc modelling performed using the SPRINT NCI and ICR data and the adult NF1 NCI study response rates. The ORR of 0% in the placebo arm is assumed because at the end of Cycle 16, patients randomised to placebo will only have received 4 cycles of selumetinib post-crossover, therefore any response detected post-crossover at the

end of Cycle 12 will be unconfirmed. Spontaneous shrinkage $\geq 20\%$ during the first 12 cycles of placebo treatment is also not expected ([Akshintala et al 2020](#)).

Forty-two patients per arm are required for the study to have 90% power to detect a treatment difference at Cycle 12 of ≥ -2 in the 1st key secondary endpoint change from baseline of PAINS-pNF chronic target PN pain score (assuming a standard deviation of 2.8) in favour of selumetinib compared with placebo at a two-sided alpha level of 5%. To allow for approximately 20% drop out (i.e., patients without at least one post-baseline average cycle PAINS-pNF chronic target PN pain score), 106 patients with a baseline PAINS-pNF chronic target PN pain score ≥ 3 will be randomised in a 1:1 selumetinib:placebo allocation.

There is no formal sample size calculation regarding the randomisation of 40 patients with baseline PAINS-pNF chronic target PN pain score of < 3 ; however, this is deemed sufficient to ensure that the target population of adults with NF1 and symptomatic, inoperable PN (including those with little or no baseline PN pain) are represented.

By assuming 20% drop out (i.e., patients without at least one post-baseline PlexiQoL total score), 58 patients per arm will provide at least 80% power to detect a treatment difference at Cycle 12 in the 2nd key secondary endpoint change from baseline of PlexiQoL total score (assuming a standard deviation of 2.3) of at least -1.2 in favour of selumetinib compared with placebo at a two-sided alpha level of 5%. Refer to [Table 4](#) for some scenarios for the statistical power for the 2nd key secondary endpoint with different mean differences in the change from baseline of the PlexiQoL total score at Cycle 12 between the two treatment groups. This range of possible treatment effects for selumetinib that could be observed in a multinational population was extrapolated based on the differences observed in other HRQoL scores in other rare disease studies as compared to an adult selumetinib cohort (D1346C00011).

Table 4: Scenarios for the Power of the Second Key Secondary Endpoint

Mean treatment difference	Statistical power
-0.7	37%
-0.8	47%
-0.9	56%
-1	65%
-1.1	73%
-1.2	80%
-1.3	86%
-1.4	91%
-1.5	94%
-1.6	96%
-1.7	98%

If it is anticipated that 20% or more of patients (across blinded study intervention groups) withdraw prior to the end of Cycle 16 for reasons other than progression, then recruitment rates notwithstanding, enrolment will continue to randomise at least 50% of the total number of dropout patients to ensure the primary endpoint is adequately powered.

